### 9.7.2. Time to Event Analysis

Single time to event analyses will be conducted as specified under the study objectives.

CCI

Real world time to event outcomes in this study will include:

- rwEFS/rwRFS for each of the first three R/R-based lines of therapy. rwEFS will be defined as the time from the treatment initiation date (for the first line of therapy) to the date of treatment failure (TF), relapse from Complete Response (CR) or better, or death from any cause, whichever comes first. TF is defined as failure to achieve CR or better following up to 6 cycles of Mylotarg. rwRFS will be defined as the time from the treatment initiation date (for the first line of therapy) to the date of a relapse event, or death from any cause, whichever comes first.
- rwOS, from the first line of therapy through the end of record or death, whichever occurs first, and
- Duration of therapy across lines of therapy from the first line of therapy through the third R/R-based line of therapy.

The time origin for analysis of rwEFS/rwRFS is the start of therapy within each specific line of therapy, and the terminal event is the earlier of an R/R event or death. The time origin for analysis of rwOS is the start of therapy within the first line of therapy, and the terminal event is death. The time origin for analysis of duration of therapy is start of Mylotarg, and the terminal event is discontinuation of that therapy.

### 9.7.3. Methods Under Objective 1

*Objective 1: To describe the demographic and clinical characteristics as outlined in the variable list below for patients diagnosed with AML who received Mylotarg in a real-world setting.*

Descriptive analysis as detailed in [Section 9.7.1](#) will be conducted for work under this objective. Demographic characteristics that will be reported will include the distribution of sex, patient age, race/ethnicity, height, weight, BMI, insurance status, and region of residence closest to the index date. Clinical characteristics that will be reported will include the distribution of comorbidity status and comorbidity index score, ECOG score, and disease characteristics, such as stage at index date, cytogenetic testing at index date, and whether the AML diagnosis was de novo versus secondary.

Demographic and clinical characteristics will not be stratified by a primary grouping variable.

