## 3.5. Study Measures

### 3.5.1. Data Elements

#### 3.5.1.1. Curated Data

Data abstracted for eligible patients from the unstructured data available in the Definitive Oncology Dataset by CRNs will include the following:

- Race/Ethnicity ([Table 1](#)).
- Date of initial AML diagnosis. This date defines the *index date* for the study, as referenced below in describing other study variables ([Table 1](#)).
- Documentation of de novo versus secondary AML at index date. Secondary AML is defined as development of AML after myelodysplastic syndromes (MDS), myeloproliferative neoplasms (MPN), or following exposure to chemotherapy and/or radiotherapy ([Table 2](#)):
  - If secondary AML, documentation of use of hypomethylating agents (HMA) at any point prior to initial AML diagnosis (Y/N). If yes, name of HMA agent will be documented.
- Stage at index date ([Table 2](#)).
- Comorbidities, indicated as present versus not indicated as present at index date ( $\pm 30$  days). The conditions to be assessed will include those assessed as part of the standard Charlson Comorbidity Index. These include myocardial infarction, congestive heart failure, peripheral vascular disease, cerebrovascular accident, hemiplegia, chronic obstructive pulmonary disease, ulcer disease, diabetes, renal disease, connective tissue disease such as rheumatoid arthritis or lupus, Alzheimer's or other dementia, cirrhosis or other serious liver disease, leukemia (other than AML), lymphoma, metastatic solid tumor, and Human Immunodeficiency Virus (HIV)/acquired immunodeficiency syndrome (AIDS). The Charlson Comorbidity Index will be computed ([Table 2](#)).
- ECOG performance status, if available, or indication of impaired performance status not otherwise classified as an ECOG rating, at index date ( $\pm 30$  days) ([Table 2](#)).

- First response and best overall response to treatment from the index date through the end of the first R/R-based line of therapy or the end of the record, whichever occurs first (Table 9-Table 11, Table 14-Table 15).
- Biomarker status and date of results will be recorded at index date ( $\pm 30$  days) (Table 2).

Biomarkers collected will include:

- IDH1
- IDH2
- TP53
- Intermediate Risk
  - FLT3
  - NPM1.

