### 3.5.1.2. Extracted Data

Data extracted for eligible patients from the structured data that are available in the Definitive Oncology Dataset through SQL query will include the following:

- Insurance status (private only, public only, both, neither) (Table 1).
- State of residence (Table 1).
- Sex (Table 1).
- Height (Table 1).
- Weight at index date ( $\pm 30$  days) (Table 1).
- Date of birth (Table 1).
- Date of death (Table 8).

- Treatments, dates of treatments, dose, and schedule for all oral (if applicable), infused, or injected anti-cancer therapies from the index date through the end of the third R/R-based line of therapy or the end of the record, whichever comes first (Table 3-Table 5).

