### 3.5.2. Derived Variables

Variables derived from abstracted and extracted data will include the following:

- Age at index date (Table 1).
- BMI at index date ( $\pm 30$  days) (Table 1).
- Geographic census region of patient's residence (Table 1).
- Weighted index of comorbid disease condition. Weighting of comorbid conditions will follow the weighting as specified in the Charlson Comorbidity Index (Table 2).
- Start and end dates and start and end dose of infused anti-cancer treatments from the index date through the end of the third R/R-based line of therapy or the end of the record, whichever occurs first.
- Dose changes of all oral (if applicable), infused, or injected anti-cancer therapies from the index date through the end of the first R/R-based line of therapy or the end of the record, whichever occurs first (Table 4).
- Start and end schedule of infused anti-cancer treatments from the index date through the end of the third R/R-based line of therapy or the end of the record, whichever occurs first (Table 3-Table 5).
- Treatment regimens, derived from oral and infused agents delivered, including start and stop dates, and indication of subsequent treatment after 1L (Table 3-Table 5).
- Duration of anti-cancer treatments regimens from the index date through the end of the third R/R-based line of therapy or the end of the record, whichever occurs first. Duration will be calculated as the end date of a regimen minus the start date of the corresponding regimen and will be computed during the analytics phase of the project (Table 5).
- Time under observation for analysis of rwEFS/rwRFS, by line, based on start date of treatment within line and dates of R/R event or disease progression, or censoring (Table 5-Table 7).
- Time under observation for analysis of rwOS from start of the first qualifying Mylotarg-containing R/R-based line of therapy, based on start of treatment in the first qualifying line setting, and based on date of death or censoring (Table 8).

- Time to best response for each regimen in the first qualifying Mylotarg-containing R/R-based line of therapy from the index date through the end of the third R/R-based line of therapy or the end of the record, whichever occurs first (Table 9-Table 11, Table 14-Table 15).

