A discontinuation will be defined as stopping of a particular agent for any reason, as indicated by provider documentation of “discontinuation” or “change in therapy” in the medical record, or, in the absence of provider documentation of discontinuation or change in treatment, a change in treatment with a particular agent, with no further treatment with that agent documented in structured data, or, evidence that the patient is admitted to hospice care (as the assumption is made that all systemic therapy is discontinued at that time).

For purposes of this study, first line therapy will be defined as beginning with the first regimen the patient receives after diagnosis of the disease of interest. Subsequent lines in this study will be defined as *R/R-based lines*. *R/R-based lines* are defined by the occurrence of an R/R event or a disease progression - either may be cited, in which an R/R event or disease progression must occur for a new regimen to be interpreted as a new line of therapy. In this study, **refractory** AML is defined as disease that is nonresponsive or failing to achieve at least minimal response while on therapy. **Relapsed** status is defined as the recurrence or worsening of disease following achievement of at least a minimal response. Additionally, the documentation of advancement of disease in patients after initial AML diagnosis but before initial AML treatment will be interpreted as a disease progression. R/R events and disease progression will be defined based on provider documentation, which primarily includes progress notes.

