rwEFS will be defined as the time from the treatment initiation date (for the first line of Mylotarg-containing therapy) to the date of treatment failure (TF), relapse from CR or better, or death from any cause, whichever comes first. TF is defined as failure to achieve CR or better following up to 3 cycles of Mylotarg. Accordingly, the time origin for rwEFS will be the start of Mylotarg in the first line of therapy in which it is used. The terminal event for analysis of rwEFS is the earlier of treatment failure, relapse from CR or better (as evidenced by provider documentation), or death. Patients who have not died or experienced an event by the date of last contact within the medical record will be censored for analysis of rwEFS.

rwRFS will be defined as the time from the treatment initiation date (during the first line of Mylotarg-containing therapy) to the date of a relapse event, or death from any cause, whichever comes first. The time origin for rwRFS will be the start of Mylotarg in the first line of therapy in which it is used. The terminal event for analysis of rwRFS will be the earlier of a relapse event (as evidenced by provider documentation), or death. Patients who have not died or experienced a relapse event by the date of last contact within the medical record will be censored for analysis of rwRFS.

The time origin of rwOS analysis is the start of the first Mylotarg use. The terminal event for analysis of rwOS is date of death. Note that Social Security Disability Insurance (SSDI) records have an expected lag of up to 4 months. Accordingly, patients who are not indicated to be deceased in clinical records or SSDI records will be censored for rwOS analysis as of the later of 1) the latest date known alive within the clinical record, 2) 4 months prior to the date of most recent SSDI update.

Separate Kaplan-Meier analyses will be conducted for each rwEFS, rwRFS and rwOS endpoint.

#### 4.3.6. Methods under Objective 4

*Objective 4: To evaluate response among AML patients who received Mylotarg in a real-world setting.*

- a. First and best response for each regimen in the first qualifying Mylotarg-containing R/R-based line of therapy.
- b. Time to best response for each regimen in the first qualifying Mylotarg-containing R/R-based line of therapy.
- c. Duration of best response for each regimen in the first qualifying Mylotarg-containing R/R-based line of therapy.

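### Treatment failure is an rwEFS event in SAP 4.3.5, but it has no derivation rule or date and is absent from the rwEFS time variable; built as SAP 3.5.2 and 4.3.2 state, rwEFS is biased upward

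*SAP*

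**What the plan says.** **Event definition.** SAP 4.1 names rwEFS among the primary endpoints. SAP 4.3.5 states: "The terminal event for analysis of rwEFS is the earlier of treatment failure, relapse from CR or better", or death. The definition of TF appears in both 4.3.2 and 4.3.5: "TF is defined as failure to achieve CR or better following up to 3 cycles of Mylotarg". Protocol 9.7.2 gives a different limit: "TF is defined as failure to achieve CR or better following up to 6 cycles of Mylotarg".

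**Derivation.** SAP 3.5.2 describes the rwEFS/rwRFS time variable as "based on start date of treatment within line and dates of R/R event or disease progression, or censoring". The definition bullet in SAP 4.3.2 includes TF, but the closing paragraph of the same section gives the terminal event as an R/R event or death.

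**Labels.** SAP 4.2 defines refractory disease as nonresponsive or "failing to achieve at least minimal response while on therapy". It defines relapse as recurrence or worsening after at least a minimal response.

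**Data.** SAP 3.5.1.1 collects "First response and best overall response to treatment", in a window that closes with the first R/R-based line. SAP 4.3.6 collects the date of best response for each regimen in the first Mylotarg-containing line. SAP 3.5.1.2 extracts "Treatments, dates of treatments, dose, and schedule for all oral (if applicable), infused, or injected anti-cancer therapies". No curated, extracted or derived item is a Mylotarg cycle count, a TF flag or a TF date.

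**Censoring.** SAP 4.3.5: "Patients who have not died or experienced an event by the date of last contact within the medical record will be censored" for rwEFS.

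**The concern.** The thresholds for the two kinds of failure differ. A patient avoids TF only by reaching CR, but avoids the refractory label with any minimal response. A patient with a PR that never deepens is therefore a TF under 4.3.5 and need not have an R/R date. Section 4.3.5 counts this patient as an event. A program written from 3.5.2 and the closing paragraph of 4.3.2 would not, and the patient would contribute event-free time until worsening, death or last contact.

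The SAP's cross-references from data items to tables point the same way. Response is mapped to Tables 9-11 and 14-15, and extracted treatment dates to Tables 3-5. Of the rwEFS tables (6 and 13), neither item is mapped to either one. R/R and progression dates are mapped to Tables 6-15.

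The result for a primary endpoint would then depend partly on how often physicians write an R/R or progression statement for patients short of CR.

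**Working it through.** The documents give no expected rwEFS, event count or power, so there is no planned figure to reproduce. The calculation below is illustrative.

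**Inputs from the documents**
- n = 20-30 (SAP 3.3).
- Background CR rate 60-70% (SAP 1); this is not a study assumption.
- 21-day cycle, stated only for the regimen-gap rule (SAP 4.2).

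**Inputs assumed**
- Exponential times.
- Median 12 months to relapse or death after CR, and 6 months to death without CR.
- TF, or an R/R label standing in for it, dated at month 2.
- A share u of non-CR patients with no R/R or progression date.
- No worsening of unlabelled patients before death.

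**Patients affected.** 20 × 0.30 = 6, up to 30 × 0.40 = 12.

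**6-month rwEFS.** After the TF date, with CR share c, S(t) = c·2^(−t/12) + (1−c)·u·2^(−t/6). At c = 0.6 and t = 6, S = 0.6 × 0.707 + 0.4 × u × 0.5 = 0.424 + 0.2u.

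**Median.** Put x = 2^(−t/12) and solve 0.4u·x² + 0.6x − 0.5 = 0; then t = 12·log2(1/x).

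| u | 6-month rwEFS | x | median (months) |
|---|---|---|---|
| 0 (every TF dated) | 0.424 | 0.833 | 3.2 |
| 20% | 0.464 | 0.757 | 4.8 |
| 40% | 0.504 | 0.702 | 6.1 |
| 60% | 0.544 | 0.659 | 7.2 |

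At c = 0.5 the 6-month value moves from 0.354 to 0.404-0.504 for u = 20-60%. At c = 0.7 it moves from 0.495 to 0.525-0.585.

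**Wider assumptions.** Take u = 50%, CR 60-70%, and median death without CR of 6 to 9 months. The 6-month excess is (1−c) × 0.5 × 2^(−6/m), where m is that median. It runs from 0.3 × 0.5 × 0.5 = 0.075 to 0.4 × 0.5 × 0.63 = 0.126, about 8 to 13 points.

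**Does the TF date matter?** The 6-month value does not change for any TF date before month 6, by construction. SAP Table 6, however, reports the median and its interval, with no 6-month rate. With every TF dated at month d, the median equals d whenever c·2^(−d/12) is at or below 0.5.
- At d = 2 this holds for c below 0.5 × 2^(2/12) = 0.56.
- At c = 0.5, dating TF at month 0, 2 or 3 gives a median of 0, 2 or 3 months.
- At c = 0.6, dating at 3 × 21 = 63 days (2.07 months) gives 3.16 months. Dating at 6 × 21 = 126 days (4.14 months) gives 4.14 months.

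**Opposite error.** Suppose a share f of true CR patients has no documented CR and is scored as TF. At c = 0.6, S(6) = 0.6 × (1−f) × 0.707, which is 0.382 at f = 10% and 0.339 at f = 20%, against 0.424. Over CR 60-70% and CR-patient medians of 12-18 months, the fall is about 4-6 points at f = 10% and 8-11 points at f = 20%.

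**The case against.** A reader might infer that TF cannot be derived from the data at all. The documents do not support that. Administration dates and schedules are extracted (SAP 3.5.1.2), best response is dated for each regimen in the first Mylotarg-containing line (SAP 4.3.6), and Protocol 9.3.2 adds the date of first positive response. TF status and an approximate date can be built from these; what is missing is the rule. One real data conflict remains. The response window in SAP 3.5.1.1 closes with the first line, although Mylotarg may first be given in line 2 or 3 and Tables 9 and 10 have columns for those lines.

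A reader might also infer that rwEFS will read too high whatever is done. That is not supported either. SAP 4.3.5 names TF as a terminal event and censors only patients without an event, so a program that follows 4.3.5 alone would count it. The upward bias follows only from the 3.5.2 and 4.3.2 wording. Scoring undocumented response as failure would push rwEFS down.

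Two further objections have weight. Worsening after a minimal response is a relapse under SAP 4.2, and progression dates are collected, so many unlabelled patients would have an event before death. The illustration ignores this and overstates the gap. The unlabelled share also has no source in the documents. At n = 25 and 60% CR there are 10 non-CR patients, so 20-60% means 2 to 6 people, and a shift of 0.04-0.12 compares with a standard error of about √(0.42 × 0.58 / 25) = 0.10.

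None of this removes the contradiction: two sections would drop events that a third counts.

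**Conclusion.** The point holds as a missing rule plus an inconsistency between sections. SAP 4.3.5 counts TF. SAP 3.5.2 and the closing paragraph of 4.3.2 leave it out, and nothing listed gives its status, cycle basis or date. If rwEFS is built as 3.5.2 and 4.3.2 state, it is biased upward. For 20-60% unlabelled at 60% CR, the illustrative size is 4-12 points at 6 months, with the median moving from 3.2 to 4.8-7.2 months. These are upper-end figures under assumed medians and unlabelled shares, because later worsening is ignored. About 6 to 12 of the 20-30 patients would depend on the rule if the background CR rate applied. It would be wrong to conclude from the stable 6-month value that the TF date is a detail, since it can determine the median that Table 6 reports.

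**What to change.** 1. Add to SAP 3.5.2 a Mylotarg cycle number built from the extracted administration dates, a TF status and a TF date with a stated dating rule. Name the TF date in the rwEFS time derivation.
2. Align SAP 3.5.2 and the closing paragraph of 4.3.2 with 4.3.5, so that one event list governs rwEFS.
3. Extend the response window in SAP 3.5.1.1 to the first Mylotarg-containing line, so that it agrees with 4.3.6.
4. Keep not-evaluable or undocumented response separate from documented non-CR, and do not score it automatically as TF. This fits SAP 4.4, under which absent data are generally reported as not documented, without imputation.
5. Report the number of TF events with no R/R label. Add sensitivity analyses on the TF date and on undocumented response scored as TF versus not.
6. The sponsor must reconcile the 3-cycle limit in the SAP with the 6-cycle limit in the protocol; no view is taken here on which applies.

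The cost is SAP wording, some programming on dates largely already collected, and chart re-checks for non-CR patients in a study of 20-30. The reported rwEFS is likely to be less favourable than one built on R/R dates and death alone.

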Demographic and clinical characteristics will not be stratified by a primary grouping variable.

#### 4.3.4. Methods under Objective 2

*Objective 2: To describe the treatment patterns from the diagnosis of AML through the end of the third R/R-based line of therapy.*

Analysis under this objective will include all study patients. Descriptive analysis as detailed in [Section 4.3.1](#) will be conducted for work under this objective. Treatment patterns include description of regimens within line of therapy for the first 3 R/R-based lines of systemic therapy as well as the description of sequences of regimens across the first 3 R/R-based lines of systemic therapy. Description of treatment regimens within line includes the frequency and percentage of each agent/regimen received, by regimen in sequence, by line, for the first 3 R/R-based lines of systemic therapy. In addition, the analysis will descriptively characterize the starting dose and dose changes of Mylotarg in each of the first lines of therapy.

Duration of treatment will also be descriptively analyzed across lines of therapy, starting with the first agent or regimen in the first line of therapy for the first 3 R/R-based lines of therapy.

### 4.3.5. Methods under Objective 3

*Objective 3: To describe the effectiveness outcomes of treatment of AML patients who received Mylotarg in a real-world setting*

Analysis under this objective will include all study patients. The outcomes of interest under this objective are rwEFS/rwRFS and rwOS. Time to event analysis as described in [Section 4.3.2](#) will be utilized.

The Kaplan-Meier product limit estimator will be employed to evaluate rwEFS/rwRFS and rwOS. The time origin for these analyses will be the start of the treatment in the respective line of therapy for rwEFS/rwRFS for the first 3 R/R-based lines of therapy. The time origin of rwOS analysis is the start of the earliest line of Mylotarg therapy. rwEFS/rwRFS and rwOS analyses for lines of therapy will be limited to patients who received treatment during the line of interest.

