**Table 7. Kaplan-Meier Analysis of rwRFS from Initiation of First Mylotarg-Containing Line of Therapy, All Patients**

	N=xxx
No. of Events/No. of Patients	xxx/xxx
Median (months)	x.x
95% CI of Median	[x.x, x.x]

The time origin was the line of therapy in which Mylotarg treatment initiated.

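### rwRFS covers all patients from the start of Mylotarg, so patients with no response count as relapse-free until death or last contact, and the median is not relapse-free survival

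*SAP*

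**What the plan says.** **Population.** SAP 4.3.5: "Analysis under this objective will include all study patients. The outcomes of interest under this objective are rwEFS/rwRFS and rwOS". The one restriction is that by-line analyses "will be limited to patients who received treatment during the line of interest"; response is not required. The Table 7 shell is titled "Kaplan-Meier Analysis of rwRFS from Initiation of First Mylotarg-Containing Line of Therapy, All Patients", and Figure 2 matches it.

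**Time origin.** SAP 4.3.5: "The time origin for rwRFS will be the start of Mylotarg in the first line of therapy in which it is used". SAP 4.3.2 and Protocol 9.7.2 start the clock at first-line treatment in one sentence and at the start of each line in another. All of these are treatment starts; none is a remission date.

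**Event and censoring.** SAP 4.3.5: "The terminal event for analysis of rwRFS will be the earlier of a relapse event (as evidenced by provider documentation), or death". Then: "Patients who have not died or experienced a relapse event by the date of last contact within the medical record will be censored". Treatment failure is an event for rwEFS but not for rwRFS.

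**Competing event text.** SAP 4.3.2 and Protocol 9.7.2 first define rwRFS by relapse or death, then give a joint terminal event for rwEFS and rwRFS: a relapsed/refractory (R/R) event or death. Protocol 9.7.5 adds disease progression.

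**Meaning of relapse.** In SAP 4.2, relapsed "status is defined as the recurrence or worsening of disease following achievement of at least a minimal response". Refractory disease is defined separately, as disease that does not reach even that level of response.

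**Standing.** SAP 4.1 lists rwRFS among the primary endpoints.

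**The concern.** Relapse is conditional on a prior response, but the risk set and the clock are not. Under SAP 4.3.5 a patient whose leukemia never responds has only one possible rwRFS event, death. That patient's contribution is overall survival under another name. A responder's contribution runs from first dose, so it adds time to response to time in response. The resulting curve blends two quantities in proportions set by the response rate.

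The reported median would therefore move with the response rate and with how long non-responders live, neither of which a relapse endpoint should measure. Both documents say the rwEFS/rwRFS definition is aligned as far as possible with the sponsor's other studies, so a reader may well set this median beside others.

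No other shell clearly supplies the missing quantity. Table 11 (duration of best response) also carries a footnote placing its time origin at the line of therapy in which Mylotarg was started.

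**Working it through.** The documents give no rwRFS figure to reproduce. The check has three parts.

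**1. What each text does with each kind of patient**

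| Patient | SAP 4.3.5 (relapse or death) | SAP 4.3.2; Protocol 9.7.2, 9.7.5 (R/R event or death) |
|---|---|---|
| No response | At risk until death or last contact | Event when declared refractory |
| Partial response, then worsening | Relapse event | R/R event |
| Remission, then relapse | Event; time includes pre-remission period | Same |

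The left column mixes in survival of non-responders. The right column is a form of event-free survival. Neither is relapse-free survival among patients in remission.

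**2. How many patients enter without a complete remission**

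Inputs: N = 20-30 (SAP 3.3); remission rate p = 60-70% after induction chemotherapy (SAP 1). Count = N × (1 − p).

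- N = 20: 20 × 0.30 = 6 to 20 × 0.40 = 8.
- N = 30: 30 × 0.30 = 9 to 30 × 0.40 = 12.

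That leaves 12-14 of 20, or 18-21 of 30, in remission.

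At this rate, 6-12 is an upper bound on those who cannot relapse, because a partial responder can. The rate itself is for induction; Mylotarg first given in line 2 or 3 also qualifies (SAP 3.4.1), and the rate there may differ.

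**3. Illustrative medians**

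These inputs are assumptions, not figures from the documents: remission at 1.5 months; exponential time from remission to relapse or death with median 10 months; exponential survival in non-remitters with median m = 4, 8 or 12 months; remission rate widened to 50-70%. For simplicity non-remitters are given death as their only event.

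Under SAP 4.3.5 the median t solves

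p × 2^(−(t − 1.5)/10) + (1 − p) × 2^(−t/m) = 0.5.

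Example, p = 0.5 and m = 4: at t = 6.8 the terms are 0.346 + 0.154 = 0.500.

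| Remission rate | m = 4 | m = 8 | m = 12 |
|---|---|---|---|
| 50% | 6.8 | 9.7 | 11.7 |
| 60% | 7.6 | 10.0 | 11.7 |
| 70% | 8.5 | 10.4 | 11.6 |

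In every cell the remitters' median is 10.0 months from remission, or 1.5 + 10 = 11.5 from treatment start.

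Under the R/R-event text, suppose refractory patients have their event by 63 days (assumed; 3 cycles from the SAP's treatment-failure wording × 21 days). After that only remitters remain, so t = 1.5 + 10 × log2(2p). This gives 1.5 + 2.6 = 4.1 months at 60% and 1.5 + 4.9 = 6.4 months at 70%. The reported median therefore also depends on which sentence is programmed.

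**The case against.** The strongest reply is that rwRFS is defined explicitly, from treatment initiation, in both documents. Nowhere do they say it is meant to show how long remission lasts. Duration of best response is a separate objective, the study is descriptive, and no comparisons are planned. On that view this is mainly a naming matter. It stands in part: a treatment-start endpoint in all patients is a legitimate choice, but not under the label relapse-free survival, and no rationale is given for it.

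Three stronger readings are tempting, and the documents do not support them.

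- *Everyone who misses remission is unable to relapse.* SAP 4.2 asks only for a minimal response, so a partial responder can relapse. Only patients with no response cannot.
- *Refractory patients certainly count as relapse-free until death.* That follows from SAP 4.3.5. Under the R/R-event sentence in SAP 4.3.2, which 4.3.5 also invokes, they leave with an event.
- *The median is biased upward.* Non-responders who die early pull it down. The values above 11.5 in the table are at most 0.2 month above the remitters' median on the same clock, so the apparent excess over 10.0 there is almost wholly the 1.5-month shift in origin.

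Sampling error is also large. For 25 uncensored patients, binomial limits for the median are the 8th and 18th ordered times. With an exponential median of 10 these lie near 10 × log2(26/18) = 5.3 and 10 × log2(26/8) = 17.0 months, wider than the whole 6.8-11.7 range. That limits the practical weight of the illustration. It does not change what is being estimated.

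**Conclusion.** The point holds. Followed as written, SAP 4.3.5, Table 7 and Figure 2 report a primary endpoint that is not relapse-free survival, because the risk set includes patients who by SAP 4.2 cannot relapse and the clock starts before anyone has responded. The competing event text does not repair this; it turns rwRFS into a form of event-free survival.

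This conclusion rests on the wording alone. The size does not: the patient count borrows an induction-chemotherapy remission rate, and the medians rest on assumed timing and survival. What the illustration does show is that the median can fall on either side of the 10.0 months from remission, depending on non-responders' survival and the response rate. For a descriptive study of 20-30 patients this should be corrected before analysis, but it does not undermine the other endpoints.

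**What to change.** Change SAP 4.3.2, 4.3.5, Table 7 and Figure 2 as follows.

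1. Restrict rwRFS to patients with a documented remission in the first Mylotarg-containing line.
2. Name the qualifying categories and make them consistent with rwEFS and with one overall-response definition. rwEFS now uses CR or better; overall response is CR, CRi or MLFS in SAP 4.3.6 but CR, CRh or CRi in the footnotes to Tables 9 and 10.
3. Start the clock at the first documented date of that remission. Restricting the population without moving the origin would leave guaranteed event-free time before remission.
4. Keep relapse or death as the only events, and reconcile the R/R-event sentence in SAP 4.3.2.
5. Replace the all-patients label on Table 7 and Figure 2 with the remitter group and its n. rwEFS continues to cover all patients.
6. Extend response-date abstraction to the first Mylotarg-containing line, whichever line that is, and include the first remission date. SAP 3.5.1.1 stops response collection at the end of the first R/R-based line. Protocol 9.3.2 collects dates of first positive and best response, and neither need be the first remission.

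Align Protocol 9.7.2 and 9.7.5. Protocol 9.7 says major changes to primary endpoint definitions would be reflected in an amendment, so one may be needed.

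If the sponsor prefers the all-patient, treatment-start version, rename it so that it is not called relapse-free survival, and state how refractory patients are handled.

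The cost is wording, some added abstraction and possibly an amendment. rwRFS would rest on about 12-21 patients with a wider interval. For 12 uncensored patients the limits are the 3rd and 10th ordered times, near 10 × log2(13/10) = 3.8 and 10 × log2(13/3) = 21.2 months under the same assumed median of 10.
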